#### 9.3 Tabulation of Individual Response Data

Listings of SAEs, AEs and AEs resulting in treatment discontinuation will be provided.

## 9.4 Exploratory Analyses

Spearman correlations and scatterplots are provided to assess the correlation of TNF activation score and urinary MCP1/uCr and urinary TIMP1/uCr biomarker levels at baseline, and the correlation of uEGF/uCr at baseline with changes and percent changes in urinary MCP1/uCr and urinary TIMP1/uCr biomarker levels and in eGFR and UPCR values at week 10.

Continuous outcomes (e.g., eGFR, uEGF/uCr biomarker levels) will be summarized descriptively, including baseline, follow-up and changes from baseline and graphically as spaghetti plots of participants' changes (absolute and relative) over time and values over time.

## 9.5 Sample Size

No formal sample size calculations were performed (either for estimation or hypothesis testing) because this study is a pilot investigation of urine biomarkers for target engagement of TNF inhibition. Rather, we assessed the magnitude of effects that can be detected in urine biomarkers using a paired t-test. With 7 patients, 80% power, and a two-sided type I error of 10%, we can detect an effect size (change from baseline to week 10 / SD) of 1.2 of changes in urinary TIMP1/uCr and of changes in urinary MCP1/uCr, with no adjustments for multiplicity (EAST 6.2).

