10.3 DESCRIPTION OF STATISTICAL METHODS

10.3.1 GENERAL APPROACH

Analyses are primarily descriptive in nature in this pilot study. Continuous variables will be summarized using descriptive statistics including n, mean, median, standard deviation, interquartile range (i.e., 1st and 3rd quartiles), and range (i.e., minimum and maximum). Qualitative variables will be summarized using counts and percentages. Unless otherwise specified, statistical analyses will be performed using SAS Version 9 or higher. Where appropriate, statistical tests will be conducted at the 0.05 significance level using two-tailed tests and p-values will be reported.

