10.3.2 ANALYSIS OF THE PRIMARY EFFICACY ENDPOINT(S)

The change in urine MCP1/Cr and TIMP1/Cr levels from baseline to study week 10, i.e. 2 weeks after the final dose of adalimumab, are the primary endpoints. We will provide tabular and graphical summaries of the changes from baseline to week 10 in MCP1/Cr and in TIMP1/Cr, including summaries at baseline and week 10. The changes from baseline to week 10 in urine MCP1/Cr and TIMP1/Cr levels will be tested using the paired t-test or Wilcoxon signed-rank test (if distributional assumptions are not met).

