10.4 SAMPLE SIZE

No formal sample size calculations were performed (either for estimation or hypothesis testing) because this study is a pilot investigation of urine biomarkers for target engagement of TNF inhibition. Rather, we assessed the magnitude of effects that can be detected in urine biomarkers using a paired t-test. With 6 patients, 80% power, and a two-sided type I error of 10%, we can detect an effect size (change from baseline to week 10 / SD) of 1.2 of changes in uTIMP1/Cr and of changes in uMCP1/Cr, with no adjustments for multiplicity (EAST 6.2).

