#### **Hypothesis:**

TNF inhibition with adalimumab (Humira) in patients with up-regulation of the intra-renal TNF pathway results in reduction in urinary MCP1/uCr and/or TIMP1/uCr biomarker levels.

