#### 7.6 Multiple Testing

Statistical testing is conducted at the 0.05 significance level using two-tailed tests; two-sided p-values are reported. No adjustments for multiplicity are planned for this pilot study. Rather, inferences and decision-making are based primarily on the magnitude of treatment effects.

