## 9. Statistical Methods

## 9.1 Analyses of Primary Endpoints

The changes in urinary MCP1/uCr and urinary TIMP1/uCr levels from baseline to study week 10, i.e., 2 weeks after the final dose of adalimumab, are the primary endpoints. We provide tabular and graphical summaries of the changes from baseline to week 10 in urinary MCP1/uCr and in urinary TIMP1/uCr, including summaries at baseline and week 10. The changes from baseline to week 10 in urinary MCP1/uCr and urinary TIMP1/uCr levels will be tested using the Wilcoxon signed-rank test.

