## 4. Change in analysis of the primary endpoints

The nonparametric approach was considered more appropriate for the small sample size.

Protocol: Section 10.3.2 ANALYSIS OF THE PRIMARY EFFICACY ENDPOINT(S).

The changes from baseline to week 10 in urinary MCP1/uCr and TIMP1/uCr levels will be tested using the paired t-test or Wilcoxon signed-rank test (if distributional assumptions are not met).

**SAP:** Section 9.1 Analyses of Primary Endpoints.

The changes from baseline to week 10 in urinary MCP1/uCr and urinary TIMP1/uCr levels will be tested using the Wilcoxon signed-rank test.

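### The SAP's stated sensitivity (80% power at effect size 1.2) is for a paired t-test at 10%; the planned test, a signed-rank test at 5%, has about 72% power with 7 patients and 48% with 6

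*SAP*

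**What the plan says.** **SAP 9.5** disclaims a formal sample size calculation, then gives a detectable effect for a paired t-test: "With 7 patients, 80% power, and a two-sided type I error of 10%, we can detect an effect size" (mean change over SD of change) of 1.2 in each biomarker, unadjusted for multiplicity.

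**SAP 9.1** names one test for the primary endpoints: the changes in both biomarker "levels will be tested using the Wilcoxon signed-rank test". The list of changes in SAP section 10 (item 4) records that the t-test option was dropped on purpose: "The nonparametric approach was considered more appropriate for the small sample size".

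**SAP 7.6** sets the level: "Statistical testing is conducted at the 0.05 significance level using two-tailed tests; two-sided p-values are reported". SAP section 8 repeats it.

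**Protocol 10.4** has the same statement with one number different: "With 6 patients, 80% power, and a two-sided type I error of 10%, we can detect an effect size" of 1.2. Protocol 10.3.1 also sets 5%: "Where appropriate, statistical tests will be conducted at the 0.05 significance level using two-tailed tests and p-values will be reported". Protocol 10.3.2 keeps the t-test as the default, with changes "tested using the paired t-test or Wilcoxon signed-rank test (if distributional assumptions are not met".

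Up to 8 patients are treated, to secure at least 6 evaluable (Protocol 4.1, SAP 1.1).

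**The concern.** Three things in SAP 9.5 do not fit the rest of the plan.

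1. It uses a two-sided 10% level; testing is at two-sided 5%.
2. It uses a paired t-test; the SAP will run only the signed-rank test.
3. It uses 7 patients with the effect size that belonged to the protocol's 6.

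The first two overstate sensitivity and the third understates it. In the protocol only the level conflicts, because the t-test is its default test.

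The signed-rank test is discrete, which matters with so few patients. A reader relying on 9.5 would take a non-significant p-value as coming from a test with 80% power at 1.2, and could read it as evidence against target engagement. At the minimum sample, that test would miss such an effect about half the time.

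**Working it through.** **Inputs.** Effect size 1.2, power 80%, two-sided 10%, n = 7 (SAP 9.5) or n = 6 (Protocol 10.4). Planned test: signed-rank (SAP 9.1), two-sided 5% (SAP 7.6 and 8). The documents give no SD or distribution for the changes and do not say whether p-values are exact. I assume normal changes and exact p-values, then vary both.

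**Step 1: the plan's own figure.** Paired t-test power comes from the noncentral t with n − 1 degrees of freedom and noncentrality 1.2 × √n.

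- n = 7, 10%: noncentrality 3.175, critical value 1.943, power 87.4%. The effect detectable with 80% power is 1.07.
- n = 6, 10%: noncentrality 2.939, critical value 2.015, power 80.8%. The effect detectable with 80% power is 1.19.

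So 80% at 1.2 reproduces for the protocol's 6 patients and not for the SAP's 7. At 5% the t-test gives 75.4% (n = 7) and 65.5% (n = 6; 80% power needs 1.43).

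**Step 2: what the signed-rank test needs.** Under the null hypothesis all 2ⁿ sign patterns are equally likely.

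- n = 5: the smallest two-sided p is 2/32 = 0.0625, so 5% cannot be reached.
- n = 6: the smallest p is 2/64 = 0.031. If the smallest change alone goes the other way, p = 4/64 = 0.0625. Only six changes in one direction are significant.
- n = 7: rejection when the smaller rank sum is 2 or less; attained level 2 × 3/128 = 0.047.
- n = 8: rejection when it is 3 or less; attained level 2 × 5/256 = 0.039.

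**Step 3: power of the planned test at 1.2.** For n = 6 there is a closed form: Φ(1.2)⁶ = 0.8849⁶ = 0.480 (the opposite tail is negligible), and the 80%-power effect is Φ⁻¹(0.8^(1/6)) = 1.79. The n = 7 and n = 8 figures are from simulation.

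| n | Paired t, 10% | Exact signed-rank, 5% | Effect for 80% power, signed-rank 5% | Exact signed-rank, 10% |
|---|---|---|---|---|
| 6 | 80.8% | 48% | 1.79 | 78% |
| 7 | 87.4% | 72% | 1.33 | 82% |
| 8 | 91.9% | 77% | 1.25 | 88% |

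Like for like, power falls from 81% to 48% at n = 6 and from 87% to 72% at n = 7. Most of the loss comes from the level: at 10% the signed-rank test is close to the t-test.

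**Step 4: varying the assumptions (5% level, effect 1.2).**

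- Normal-approximation p-values: 69% (n = 6), 72% (n = 7) and 83% (n = 8) uncorrected; 48%, 62% and 77% with continuity correction.
- Heavier tails (scaled t, 5 df), exact test: 56% (n = 6), 77% (n = 7).
- Skewed changes (standardised gamma, shape 2 or 4, either direction), exact test: from 47% to just under 80% (n = 6), 68% to 97% (n = 7).
- At least one of the two biomarkers significant, both at 1.2, normal changes, exact test, correlation from 0.8 down to 0: 62% to 73% (n = 6), 82% to 92% (n = 7).

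**The case against.** **Little depends on the sentence.** The SAP says no formal calculation was made, calls the analyses mainly descriptive and bases decisions on the size of effects. Enrolment was not derived from 9.5, and the SAP describes treatment in the past tense, so better figures cannot change the design. This stands and limits the weight of the point. It does not make the sentence right: the stated aim is to test a hypothesis, both endpoints are tested at 5%, and 9.5 gives n, power, level, effect size and software for a test that will not be run.

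**The 48% is for 6 patients, while 9.5 speaks of 7.** True; at 7 the gap is from a stated 80% to about 72%. But 6 is the plan's own minimum. Filling a missing week 10 value from week 8 (SAP 7.4) makes falling to 6 less likely without ruling it out.

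**The hypothesis is satisfied by either biomarker.** SAP 3.1 predicts that treatment "results in reduction in urinary MCP1/uCr and/or TIMP1/uCr biomarker levels". With 7 patients the chance that at least one is significant is 82% to 92%, above 80%. That is a fair counterweight, but 9.5 states its figure for each biomarker, and with 6 patients the chance is 62% to 73%.

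**Normality and exact p-values are not in the documents.** Correct, and any replacement text must name them. With the uncorrected approximation, five changes in one direction give p of about 0.043, so the limit at 5 patients holds only for exact or continuity-corrected p-values. The mismatch of test and level depends on neither assumption.

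**Conclusion.** The concern holds. SAP 9.5 gives the sensitivity of a test and level that the SAP does not use, and no other section supplies the right figure. Under normal changes and exact p-values, power per biomarker at effect size 1.2 is 48%, 72% and 77% with 6, 7 and 8 patients, and 80% power needs effects of 1.79, 1.33 and 1.25. Other distributions or p-value methods move these figures, in some skewed cases well upward. The stated pairing of 7 patients with 1.2 is also wrong on its own terms (87.4% power, or 80% at 1.07). In Protocol 10.4 only the 10% level conflicts. The statement should be corrected; because the study is a descriptive pilot, the error does not threaten its design or main conclusions.

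**What to change.** **SAP 9.5.** Replace the last sentence with:

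> Each primary biomarker is tested with the exact two-sided Wilcoxon signed-rank test at 0.05, without multiplicity adjustment. Assuming normally distributed changes, power per biomarker at effect size 1.2 is 48% with 6 patients, 72% with 7 and 77% with 8; 80% power requires effect sizes of 1.79, 1.33 and 1.25. With 5 patients p ≤ 0.05 cannot be reached.

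**SAP 9.1.** Specify the exact form of the test. At n = 6 the choice between exact and uncorrected approximate p-values moves power from 48% to 69%, so it should not be left open.

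**Protocol 10.4.** Keep the t-test and align the level: with 6 patients at two-sided 5%, a paired t-test has 80% power at 1.43, and 65.5% at 1.2.

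**If 10% was the intended level**, state 0.10 in Protocol 10.3.1 and SAP 7.6 and 8. Protocol 10.4 can then stand, and SAP 9.5 should give the signed-rank figures at 0.10: 78%, 82% and 88% for 6, 7 and 8 patients, with 80%-power effects of 1.24, 1.16 and 1.06. This is a real change of significance level, made after patients were treated, and it raises the attained false-positive rate per biomarker to 8–9%. It should be chosen only if 10% was the original intent.

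**Cost.** The main fix is a few sentences, with no change to patients or data. Naming the exact test changes the analysis only if approximate p-values had been intended. The stated power becomes less favourable.

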## 10. Summary of Changes to the Protocol and/or SAP

The changes from the protocol-specified definitions of aims, outcomes and statistical analytic approaches are outlined below. These changes reflect advances in our knowledge of FSGS and MCD since the design of the study that were not incorporated as protocol amendments but were discussed during the formation of the Statistical Analysis Plan. These changes are documented herein and represent changes made prior to the database lock.

#### 1. Change in the primary aim and hypothesis

Exclusion of the hypothesis that FSGS patients with up-regulation of the TNF pathway can be identified through intra-renal gene expression profiling and assay of urinary MCP1/uCr and urinary TIMP1/uCr levels by ELISA. This is demonstrated by the successful completion of the screening protocol that determined if they were included/eligible for drug.

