2.2 RATIONALE

Based on molecular profiling, informed therapy selection targeting the underlying disturbance has been used successfully in health care and biomedical research. When successful, this forms the basis of precision medicine for the treatment of selected patient populations.

The Nephrotic Syndrome Study Network (NEPTUNE, PI [name]) study investigators have used genome wide expression profiles of renal biopsy specimens available from more than 250 patients to identify molecular subgroups of NS². Three distinct patient subgroups were identified and associated with long-term outcomes. Molecular pathway analysis of the subgroups with TR-MCD and FSGS showed activation of TNF as defined by causal inference network analysis of established downstream pathway members, including TIMP1 and MCP1 in one of the 3 subgroups. These patients presented with higher levels of proteinuria, lower levels of GFR, and more rapid progression of their glomerular disease. A TNF Z-score was computed for each NEPTUNE participant with MCD and FSGS. The score is the average Z-score of gene expression level across 145 TNF pathway genes from the tubulointerstitial compartment

of each participant's renal biopsy. Urinary MCP1 and TIMP1 were measured by ELISA from their baseline study visit and normalized to urine creatinine. Correlations of TNF gene expression Z-score with urinary biomarkers are shown in Figure 1 and distributions of these measures in boxplots from TNF z-score < 0 vs > 0 are plotted in Figure 2.

Figure 2: Scatter plot of TNF z- score and urinary TIMP1/Cr, A: All FSGS and MCD patients (corr = 0.47, P<0.001) TNF z-score and urinary MCP1/Cr, B: All FSGS and MCD patients (corr = 0.51, P<0.001) TNF z-score and urinary TIMP1/Cr ng/mg. (L. Mariani, et al 2017)

[figure not shown]
[figure not shown]

Figure 3: Distribution of biomarker level by TNF Z-score category. Difference in means was statistically significant (TIMP1, p-value 0.009; MCP1 p-value 0.001) (L. Mariani, et al 2017)

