A logistic model was fit with the outcome of TNF Z-score >0 to assess the predictive ability of urinary biomarkers individually and combined. Results are shown in Table 1 for the subgroup of participants with eGFR >45. Model 3, which included both biomarkers as predictors had the highest positive predictive value and correct classification. Correctly classified was calculated by assigning those with an estimated probability of disease >= 50% as having disease and then calculating the % that are correctly classified as having and not having disease (true TNF Z-score > vs <= 0) using a patient sample with eGFR > 45 and either FSGS or MCD.

participants with editives								
	Model 1 c-statistic 0.79		Mod	del 2	Mod	el 3		
Patients with eGFR >45			c-statis	tic 0.79	c-statist	tic 0.82		
(n = 49; 13 Events)	PPV 33%		PPV	67%	PPV	75%		
	correctly classified 69%		Correctly cla	assified 78%	Correctly Cla	ssified 82%		
	OR P-value		OR	P-value	OR	P-value		
Log2(uTIMP/Cr)	1.79	0.017			1.54	0.07		
Log2(uMCP/Cr)			2.31	0.008	1.81	0.08		

Table 1: Results of Multivariable Logistic Models of TNF Z-score >0 in NEPTUNE FSGS and MCD participants with eGFR>45

Because both biomarkers contributed to greater predictive accuracy, both will be measured for patient selection into the clinical trial. The coefficients from the multivariable model will be used to calculate the odds of having a TNF Z-score >0 for each person. Odds are then converted to probability and patients with a probability >= 50% of having a positive TNF Z-score would be eligible for enrollment. Mathematically, the following equations will be used to calculate the probabilities for study inclusion:

- 1. Constant + [log2(uTIMP1/Cr) * Coef1] + [log2(uMCP1/Cr) * Coef2] = log Odds
- 2. Exp(log Odds) = Odds
- 3. Probability = Odds / (1 + Odds)

Using the following coefficients and constant from Model 3 in Table 2:

Logistic regression	Number of obs	=	49
	LR chi2(2)	=	13.61
	Prob > chi2	=	0.0011
Log likelihood = -21.542865	Pseudo R2	=	0.2401

tnf_cat	Coef.	Std. Err.	Z	P> z	[95% Conf.	Interval]
logMCPI_uCR_ngmg	.59214	.3381858	1.75	0.080	0706919	1.254972
log2timp1_uCr_ngmg	.4325066	.2401973	1.80	0.072	0382715	.9032848
cons	-1.001269	.5091692	-1.97	0.049	-1.999222	0033157

i.e., $\log Odds = -1.001269 + 0.59214 * \log 2(uTIMP1/Cr) + 0.4325066 * \log 2(uMCP1/Cr)$.

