3 OBJECTIVES AND PURPOSE

The primary purpose of this Proof of Concept study is to test the hypothesis that TNF inhibition with adalimumab (Humira) in patients with up-regulation of the intra-renal TNF pathway will result in reduction in urinary indicators of TNF pathway activation, specifically urine MCP1/Cr and TIMP1/Cr levels.

Furthermore, this study is proposed to test the hypothesis that FSGS patients with up-regulation of the TNF pathway can be identified through intra-renal gene expression profiling and assay of urine MCP1/Cr and TIMP1/Cr levels by ELISA.

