5 STUDY ENROLLMENT AND WITHDRAWAL

5.1 PARTICIPANT INCLUSION CRITERIA

- 1. Kidney biopsy confirmed FSGS or MCD
- 2. For Minimal Change Disease patients only, history of resistance to corticosteroid therapy
- 3. Increased urinary excretion of biomarkers of TNF activation (MCP1/Cr and/ or TIMP1/Cr) at study screening
- 4. eGFR>30 ml/min/1.73 m² at screening
- 5. Urine protein:creatinine ratio ≥1.5 g/g at screening
- 6. Age 6-80 years
- 7. Weight >15kg
- 8. Stable therapy with angiotensin converting enzyme inhibitors, angiotensin receptor blockers, and oral immunosuppression agents for at least 30 days prior to enrollment
- 9. Birth control use in females of child bearing potential
- 10. Informed consent and assent if applicable

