7 STUDY PROCEDURES AND SCHEDULE

7.1 STUDY PROCEDURES/EVALUATIONS

Biopsy report: The biopsy report from the qualifying kidney biopsy will have personal identifiers redacted, labeled with the study identification number and then submitted into the study database for review and confirmation of eligible pathology of FSGS or MCD.

Archived Kidney Biopsy Tissue: 4 unstained slides from archived paraffin block kidney tissue will be submitted for gene expression profiling when available. Patients who have submitted tissue from a kidney biopsy as part of NEPTUNE study participation will not be required to have additional tissue submitted as part of this study.

Health Related Quality of Life (HRQOL): The FSGS-MCD Patient Reported Outcome (PRO) assessment will be assessed in accordance with the schedule of events table (7.2.5). The FSGS-MCD PRO assessment should be completed by the participant at each in-person study visit.

Adverse events: Adverse event assessments will be done at each study visit as detailed in Section 9. Complete medical history: The complete medical history will include a review of pertinent medical records covering details related to the patient's history of FSGS or TR-MCD provided by the patient and/or their referring physician(s).

Physical examination: A physical exam will include a review of systems and current physical findings Interval medical history: A review of medications, interval symptoms, and any changes to the patient's medical history will be reviewed and documented.

Vital signs: Vital signs will include: blood pressure, temperature (°C), height (cm), and weight (kg) will be measured.

Pregnancy Testing: For study participants of child-bearing potential, a urine pregnancy test will be performed at screening and each study visit prior to adalimumab administration.

Clinical Laboratories: A comprehensive set of laboratory results will be performed on blood and urine samples to evaluate any toxicity or adverse events associated with FSGS or TR-MCD or its treatment with the study drug.

- Comprehensive metabolic panel (Comp): including serum electrolytes, BUN, creatinine, glucose, albumin, ALT, AST, alkaline phosphatase, total bilirubin, cholesterol, total protein
- Complete blood count with differential (CBCD): including WBC, hemoglobin, hematocrit, platelet count, and differential cell count.

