## 5.2 Inclusion-Exclusion Criteria and General Study Population

#### 5.2.1 Participant Inclusion Criteria

- 1. Kidney biopsy confirmed FSGS or MCD
- 2. For Minimal Change Disease patients only, history of resistance to corticosteroid therapy
- 3. Increased urinary excretion of biomarkers of TNF activation (urinary MCP1/uCr and/or urinary TIMP1/uCr) at study screening
- 4. eGFR>30 ml/min/1.73 m^2 at screening
- 5. Urine protein to creatinine ratio ≥1.5 g/g at screening
- 6. Age 6-80 years
- 7. Weight >15kg
- 8. Stable therapy with angiotensin converting enzyme inhibitors, angiotensin receptor blockers, and oral immunosuppression agents for at least 30 days prior to enrollment
- 9. Birth control use in females of child-bearing potential
- 10. Informed consent and assent if applicable

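### SAP section 10 item 1 treats the patient-identification hypothesis as demonstrated by completed screening, but TNF eligibility was decided from urine alone, so the hypothesis was not tested

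*SAP*

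**What the plan says.** Protocol section 3 sets out, beside the treatment hypothesis, a second one, with the urine markers measured by ELISA: "FSGS patients with up-regulation of the TNF pathway can be identified through intra-renal gene expression profiling and assay of urine MCP1/Cr and TIMP1/Cr". SAP section 10 item 1 excludes this hypothesis and explains: "This is demonstrated by the successful completion of the screening protocol that determined if they were included/eligible for drug".

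The TNF part of screening is described in these places:

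- Protocol 5.1, criterion 3: "Increased urinary excretion of biomarkers of TNF activation (MCP1/Cr and/ or TIMP1/Cr) at study screening". SAP 5.2.1 repeats it: "Increased urinary excretion of biomarkers of TNF activation (urinary MCP1/uCr and/or urinary TIMP1/uCr) at study screening".
- Protocol 2.2 makes this operational through a logistic model in the two urine markers: "patients with a probability >= 50% of having a positive TNF Z-score would be eligible for enrollment".
- Protocol 7.1, on tissue: "4 unstained slides from archived paraffin block kidney tissue will be submitted for gene expression profiling when available". Protocol 7.2.1 gives the purpose of that profiling as mechanisms of disease, not eligibility. The biopsy report serves to confirm FSGS or MCD.

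Tissue and urine meet only in an exploratory Spearman correlation with scatterplots, in participants with a recent biopsy (SAP 4.3 and 9.4, Table 19, Figures 7.1 and 7.2). Neither document gives the identification hypothesis a test or a success criterion.

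**The concern.** The sentence is the SAP's present reason for closing a hypothesis, and it states a scientific result. The result does not follow, because nothing in screening compared a urine result with a tissue result. A patient who passes the urine rule is predicted to have a positive tissue score; whether the prediction is right is the very question the hypothesis asks.

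What is at stake is what the trial may claim. If the sentence carries into the report, a proof-of-concept study will be read as having validated its selection method. The primary aim in SAP 3.1 also presupposes patients with up-regulation of the intra-renal pathway, so readers should know that this status was inferred from urine.

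A linked difficulty is that the sentence rests on the screening protocol, and Protocol 2.2 gives two versions of the equation at its core.

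**Working it through.** **1. What screening decided.** The hypothesis needs two things: a tissue measure of TNF activation, and agreement between it and urine. The criteria in Protocol 5.1 and SAP 5.2.1 and the rule in Protocol 2.2 use urine MCP1/Cr and TIMP1/Cr. No inclusion or exclusion criterion uses a tissue TNF score. A patient with no tissue available could complete screening and be treated. Completion therefore carries no information on agreement.

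**2. Reproducing the rule's stated accuracy.** Inputs from Protocol 2.2, Table 1, Model 3: n = 49, 13 patients with Z-score above 0 (so 36 without), PPV 75%, correctly classified 82%, all with eGFR above 45.

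- Only 40/49 = 81.6% rounds to 82% (39/49 = 79.6%, 41/49 = 83.7%). So TP + (36 − FP) = 40, giving TP = FP + 4.
- PPV = (FP + 4)/(2·FP + 4). FP = 1 gives 5/6 = 83%, FP = 2 gives 6/8 = 75%, FP = 3 gives 7/10 = 70%. Only FP = 2 fits.
- The table is TP 6, FP 2, FN 7, TN 34. Both stated figures reproduce.
- Exact (Clopper-Pearson) 95% interval for 6/8: 34.9% to 96.8%.
- Sensitivity is 6/13 = 46% (exact 95% CI 19% to 75%). Calling every patient negative would classify 36/49 = 73% correctly.

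**3. Illustration for the treated group.** With positive predictive value p and n treated patients, treated as independent, the chance of at least one tissue-negative patient is 1 − pⁿ.

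| p | n = 6 | n = 8 |
|---|---|---|
| 0.75 | 1 − 0.75⁶ = 82% | 1 − 0.75⁸ = 90% |
| 0.35 | | 1 − 0.35⁸ > 99.9% |
| 0.97 | | 1 − 0.97⁸ = 22% |

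The value of p in this trial is not given. The rule was fitted at eGFR above 45; the trial admits eGFR above 30 with urine protein:creatinine of at least 1.5 g/g.

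**4. The two versions of the equation.** Protocol 2.2 introduces the equation with "Using the following coefficients and constant from Model 3 in Table 2". The regression output gives 0.59214 to MCP1 and 0.4325066 to TIMP1. The equation written below it gives 0.59214 to TIMP1 and 0.4325066 to MCP1.

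- exp(0.59214) = 1.81 and exp(0.4325066) = 1.54. Table 1 lists 1.81 for MCP and 1.54 for TIMP, so Table 1 agrees with the output and not with the written equation.
- Take a hypothetical patient with TIMP1/Cr 1 and MCP1/Cr 4 ng/mg, so the log2 values are 0 and 2.
 - Output: −1.001269 + 0.59214 × 2 = 0.183, probability 0.546.
 - Written equation: −1.001269 + 0.4325066 × 2 = −0.136, probability 0.466.
- These fall on opposite sides of the 50% cut-off. With the two marker values exchanged, the two results exchange.

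**The case against.** The strongest reply is that no analysis depends on the sentence. It is rationale in the SAP's list of changes. The hypothesis is absent from SAP section 3, and SAP section 9 draws no conclusion about it. The protocol never gave it a test, and the one related analysis, the exploratory correlation, is kept. The word can also be read as feasibility: patients could be screened and selected. This stands as a limit on consequence, and no estimate, test or sample size changes. It does not rescue the sentence, because the hypothesis named just before it includes gene expression profiling, which screening did not use to decide TNF eligibility.

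A reader might also infer more than the documents support:

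- *That some treated patients were probably tissue-negative.* This needs the trial's PPV, which is unknown. For 8 patients the chance of at least one falls below 50% once PPV exceeds 0.5^(1/8), about 0.92, which lies inside the interval. Protocol 2.2 says the TNF-activated subgroup had more proteinuria and lower GFR, so this trial's entry criteria could raise PPV; in-sample optimism works the other way.
- *That the trial's tissue score is undefined.* Protocol 2.2 is specific: "The score is the average Z-score of gene expression level across 145 TNF pathway genes from the tubulointerstitial compartment". SAP 6.4 does not restate the compartment, cut-off or Z-score reference set, but it refers to the NEPTUNE protocol and published methods. That is missing detail; nothing there says scores were centred within the trial.
- *That a count of tissue-positive patients is needed to interpret a null biomarker result.* Scores are already summarised at baseline (SAP 8.3) and plotted (Figures 7.1 and 7.2). Even 4 of 4 positive would give an exact interval of 40% to 100%, and tissue up to a year old does not fix TNF status at dosing.
- *That patients were misclassified at screening.* No section says which version of the equation was run.

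**Conclusion.** The point holds as a correction to what the SAP says has been shown. Completed screening supports only the statement that urine-positive patients can be found and enrolled. It does not support the statement that patients with intra-renal TNF up-regulation were identified. This follows from the eligibility text alone and needs no assumption about accuracy.

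The 90% figure is conditional on an in-sample PPV of 75% carrying over to a different population and on independence between patients; the supportable range is 22% to over 99.9%. It shows why passing the urine rule cannot stand in for a tissue result. It is not an estimate of how many treated patients lacked the target.

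The coefficient discrepancy is a definite inconsistency within Protocol 2.2 that can change eligibility near the cut-off. Its effect on actual enrolment cannot be judged from the documents.

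**What to change.** - In SAP section 10 item 1, delete the sentence and write: *This hypothesis is not formally tested in this study; tissue-urine agreement is described only in Table 19 and Figures 7.1-7.2.*
- Add a footnote to Table 19: the correlation comes from at most 8 patients selected on the same urine markers, with tissue up to 12 months old, and neither confirms nor refutes the hypothesis. When writing it, align the tissue window, which SAP 4.3 counts from baseline and SAP 6.4 from consent.
- State which version of the Protocol 2.2 equation was used for screening, and reconcile the written equation with the regression output and Table 1.
- Optional: a descriptive count, with exact 95% CI, of treated patients with recent tissue whose score is above 0. This is meaningful only if the Z-score reference set is external to the trial. Scores centred within the trial average 0, so some would fall above 0 by construction unless all were equal.

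The cost is one replaced sentence, one footnote and one clarification, with no new samples or profiling and no change to alpha, power or sample size. The downside is a less favourable statement about the hypothesis.
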